6.7 Protocol Deviations

Protocol deviations will be classified as Minor, Important/Major or Critical/Priority. For analysis and reporting purposes, deviations leading to exclusion from the PP Analysis set will include, but are not limited to: deviation from eligibility criteria, administration of prohibited medications and erroneous administration of study treatment. The criteria for grading protocol deviations will be proposed by the Quintiles Therapeutic Medical Advisor and aligned with the Baxalta Physician. All protocol deviations leading to exclusion from PP analyses are determined together with the Baxalta Physician on a case-by-case basis by the medical reviewer prior to database lock and unblinding. Subjects will be assigned to treatment groups based on actual treatment.

7. EFFICACY EVALUATION

All efficacy measures will be summarized and evaluated utilizing the PP Analysis set and repeated using the mITT Analysis set as sensitivity analysis. Listings will be presented using the ITT Analysis set,

For the Primary and Secondary analysis, visit windowing conventions will occur at Week 16 for the purpose of equivalence testing. Based on a target day of 113, a lower bound of window (day) 103 and an upper bound of window (day) 123 will be used.

If more than one visit falls within the same visit Week 16 window, the data from the visit closest to the target day will be used for the visit summary. If two visits within the same visit window are equidistant from the target day, the data from the later visit will be used for the protocol specified visit.

Data will be listed and summarized with descriptive statistics, by randomized treatment group. Further details are provided in the following sub-sections.

7.1 Analysis of Primary Efficacy Outcome Measure

The primary efficacy objective will be met by demonstrating that subjects randomized to M923 (Arm A) and those randomized to EU RPP (Arm B) have a statistically equivalent PASI75 response rate at Week 16 (Visit 7).

The primary efficacy variable is the PASI75 response rate at Week 16 (Visit 7). A PASI75 responder at Week 16 is defined as a subject who achieves at least 75% improvement in PASI score from baseline at Week 16. The primary efficacy analysis is a test for equivalence between M923 and EU RPP groups (as randomized) and will be performed on the PP analysis set. Where missing data occurs, the NRI method (see [Section 5.2](#)) will be used to impute values.

The primary efficacy objective will be met by demonstrating that subjects randomized to M923 (Arm A) and those randomized to EU RPP (Arm B), have a statistically equivalent PASI75 response rate at Week 16 (Visit 7).

7.1.1 Hypothesis Regarding Primary Efficacy Outcome Measure

All equivalence testing will be made using 90% confidence intervals (per FDA) and an equivalence margin of 18%. For the EMA, all equivalence testing will be made using 95% confidence intervals and an equivalence margin of 15%, for rationale see Protocol section 13.1

For PASI75 response rate in each individual treatment arm, 95% confidence intervals will be calculated using Clopper-Pearson method. Confidence intervals for differences in PASI75 response rate between M923 and EU RPP will be calculated using the Newcombe score method and stratified by geographic region (North America, Western Europe, and Eastern Europe/Asia). The null hypothesis of differences in PASI75 proportions of at least 15% for EMA and 18% for FDA will be rejected if the 95% confidence interval for EMA and 90% confidence interval for FDA for the difference in PASI75 is entirely contained within the equivalence margin; in this case, statistical equivalence will be declared.

7.1.2 Derivation of Primary and Secondary Efficacy Outcome Measure Using PASI

The PASI will be evaluated by a qualified investigator at the site. The PASI combines assessments of the extent of body-surface involvement in 4 anatomical regions (head [10% of BSA], arms [20% of BSA], trunk [30% of BSA], and legs [40% of BSA]) and the severity of desquamation (scaling), erythema (redness), and induration (thickness) in each region, yielding an overall score of 0 for no disease to 72 for the most severe disease. Each of the body areas is scored by itself, and then the four scores are combined into the final PASI. For each body area, the percent of area of skin involved is estimated and then transformed into a score from 0 to 6: 0 = 0% of involved area, 1 = < 10% of involved area, 2 = 10% to 29% of involved area, 3 = 30% to 49% of involved area, 4 = 50% to 69% of involved area, 5 = 70% to 89% of involved area, 6 = 90% to 100% of involved area. Severity parameters are measured on a five point scale in which 0 = None, 1 = Slight, 2 = Moderate, 3 = Severe, 4 = Very Severe. The sum of all 3 severity parameters is then calculated for each body area, multiplied by the area score for that area and multiplied by weight of respective section (0.1 for head, 0.2 for arms, 0.3 for trunk and 0.4 for legs). Subjects achieving PASI 50, 75, or 90 response are defined as having an improvement, i.e. a reduction of at least 50%, 75% or 90%, respectively, in the PASI score compared with baseline. Information required to calculate the PASI will be recorded on the eCRF by the investigator/site staff at clinic visits.

7.2 Analysis of Secondary Efficacy Outcome Measure

The analysis of the secondary efficacy outcome measures (see [Section 3.1.2](#)) will be performed on the PP population and repeated on the mITT population.

Secondary efficacy outcome measures include PASI50, PASI90, and sPGA response rate at Week 16 (Visit 7). A PASI50 (or PASI90) responder at Week 16 is defined a subject who achieves at least 50% (or 90%) improvement in PASI score from baseline at Week 16. The sPGA response rate will be described as the proportion of subjects who have achieved a clear or almost clear response (sPGA score of 0 or 1) at Week 16

At Week 16, the treatment arms (Arm A and B) will be compared using PASI50, PASI90, and sPGA response rates. For response rates in each individual treatment arm, 95% confidence intervals will be calculated using the Clopper-Pearson method. Treatment differences and corresponding 90% and 95% confidence intervals in response rates between M923 and EU RPP will be calculated using the Newcombe score method and stratified by geographic region (North America, Western Europe, and Eastern Europe/Asia). The NRI method (see [Section 5.2](#)) will be used to handle missing data.

Descriptive statistics and 95% confidence intervals for the mean of PASI total score and percentage change from baseline will be provided by treatment arm and analysis period (Arm A and B up to Week 16; Arm A, B1, and B2 after Week 16) for each scheduled time point. No imputation for missing data will be applied (observed case).

PASI50, PASI75, PASI90, and sPGA response rate and 95% confidence intervals calculated using the Clopper-Pearson method will be summarized by treatment arm and analysis period (Arm A and B up to Week 16; Arm A, B1, and B2 after Week 16) for each scheduled time point.

Figures will be created to display the response rates and mean percentage change in PASI score over time and by treatment arm and analysis period (Arm A and B up to Week 16; Arm A, B1 and B2 after Week 16).

Health-related quality of life measures, DLQI and the EQ-5D-5L, will be summarized by treatment arm and analysis period (Arm A and B up to Week 16; Arm A, B1 and B2 after Week 16) and scheduled time point.

7.2.1 Hypothesis Regarding Secondary Efficacy Outcome Measure

No formal hypothesis testing of equivalence will be performed for the comparison between M923 and EU RPP using the secondary efficacy outcome measures.

7.2.2 Derivation of Secondary Efficacy Outcome Measure

Derivation of PASI response rates are described in [section 7.1.2](#).

The static Physician Global Assessment (sPGA) is a 6-point scale ranging from 0 (clear), 1(minimal), 2(mild), 3(moderate), 4(severe) and 5(very severe). For the purpose of analysis, clear or almost clear (6-point scale) is determined by a score of 0 or 1 at a given visit.

Dermatology Life Quality Index (DLQI) and the EuroQoL 5-Dimension Health Status Questionnaire (EQ-5D-5L) derivations are described in [section 10.1](#) and [10.2](#) respectively.

7.3 Sensitivity Analyses

For the primary efficacy measure, PASI75 response rate at the Week 16 visit, sensitivity analyses will include repeating the primary analysis using:

- mITT population with NRI method for missing data,

- PP and mITT populations with mBOCF for missing data, and
- PP and mITT populations with MMRM for missing data.

8. SAFETY EVALUATION

All safety assessments will be summarized and evaluated utilizing the safety analysis set, including AEs, physical examinations, clinical laboratory evaluations, vital signs, 12-lead ECG results and injection site reactions and will be listed and summarized with number and proportion of subjects or descriptive statistics, as appropriate, by treatment arm and analysis period (Arm A and B up to Week 16; Arm A, B1 and B2 after Week 16). Subjects who withdraw from the study prematurely will have their Early withdrawal visit summarized as an individual visit. No formal hypothesis testing of safety data is planned.

Further details are provided in the following sub-sections.

8.1 Adverse Events

Adverse events will be coded using the latest version of MedDRA.

Treatment-emergent adverse events (TEAEs) are defined as AEs that started or worsened in severity on or after the first dose of study medication, until study completion/withdrawal (Week 48) or 30 days following the last M923 or EU RPP treatment for early withdrawn subjects.

All TEAEs (including SAEs, AEs related to study drug, AEs leading to withdrawal, and injection site reactions) will be presented in summary tables. Summary tables shall indicate the number of subjects who experienced adverse events. In addition, tables will be prepared to list each AE, the number of subjects in each treatment arm who experienced an adverse event at least once, and the rate of subjects with AE(s). AEs will be grouped by system organ class and preferred term. Each event will then be divided into defined severity grades (mild, moderate, severe). The tables will also divide the AEs into those considered related (a “possibly related” or a “probably related” AE will be considered as a “related AE”) to the treatment and those considered unrelated (an “unlikely related” or a “not related” AE will be considered as an “unrelated” AE). In addition a summary of subject incidence of the top 5% of AEs will be produced.

All AEs for each subject, including the same event on several occasions, will be listed, giving both MedDRA preferred term and the original term used by the investigator, system organ class, severity grade, seriousness, relation to the treatment, onset date, and stop date.

AEs that occurred before first dose of study drug will be listed separately.

The clinical safety and tolerability of the transition from EU RPP to M923 as compared with continuous use of EU RPP with regard to AEs will be evaluated with a summary of all TEAEs by treatment arm and by treatment period:

- Period 1 from Week 0 to Week 16 (included)
- Period 2 from Week 16 to Week 25 (included)
- Period 3 from Week 25 to Week 37 (included)
- Period 4 from Week 37 to Week 48 (included)
- Follow-up

The number and percentage of subjects with any AE, any related AE, any severe AE, any related severe AE, any SAE, and any related SAE, as well as the total number of events for each category, will be summarized by treatment group. The number of deaths due to an AE, hospitalization due to an AE and study discontinuation due to an AE will be summarized by treatment arm and analysis period (Arm A and B up to Week 16; Arm A, B1 and B2 after Week 16).

The number and percentage of subjects with an AE, as well as the total number of AEs, will be summarized for each treatment arm and analysis period (Arm A and B up to Week 16; Arm A and B2 after Week 16). This tabulation will be repeated by relationship and severity.

AEs that occurred before first dose of study drug will be listed separately. Any adverse events reported more than 30 days after a subject has completed or withdrawn early from the study, will not be summarized but will be listed.

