12.1.2 Assessment of Adverse Events

For the purposes of this study, each non-serious untoward medical occurrence reported by a subject undergoing study-related procedure(s) before the first M923 or EU RPP treatment will be recorded on the AE eCRF; however, these events will not be considered as AEs and will not be included in the analysis of AEs.

Each treatment-emergent AE (non-serious AE or SAE) from the first M923 or EU RPP treatment until study completion/discontinuation (Week 48) or 4 weeks following the last M923 or EU RPP treatment (for early termination subjects) will be described on the AE eCRF using the medical diagnosis (preferred), or, if no diagnosis could be established at the time of reporting the AE, a symptom or sign, in standard medical terminology in order to avoid the use of vague, ambiguous, or colloquial expressions (see definition in [Section 12.1](#)). Each AE will be evaluated by the investigator for:

- Seriousness as defined in [Section 12.1.1.1](#)
- Severity as defined in [Section 12.1.2.1](#)

- Causal relationship to IP exposure or study procedure as defined in [Section 12.1.2.2](#)

For each AE, the outcome (ie, recovering/resolving, recovered/resolved, recovered/resolved with sequelae, not recovered/not resolved, fatal, unknown) and if applicable action taken (ie, dose increased, dose not changed, dose reduced, drug interrupted, drug withdrawn, not applicable, or unknown) will also be recorded on the AE eCRF. Recovering/resolving AEs will be followed until resolution, medically stabilized, or 30 days after the study completion/termination visit, whichever comes first. If the severity rating for an ongoing AE changes before the event resolves, the original AE report will be revised (ie, the event will not be reported as separate AE). During the course of any AE, the highest severity rating will be reported.

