13.4.4.2 Safety

The methods of analysis for the secondary safety outcome measures (see [Section 8.4.2.2](#)) will be done on the safety population.

AEs will be coded using Medical Dictionary for Regulatory Activities dictionary.

Treatment-emergent adverse events (TEAEs) are defined as AEs that started or worsened in severity on or after the first dose of study medication.

All TEAEs (including SAEs, AEs related to study drug, AEs leading to discontinuation, and injection site reactions) will be summarized by System Organ Class and Preferred Term and by treatment arm (Arm A and Arms B1 and B2). All AEs will be included in the listings (non-TEAEs and TEAEs).

The clinical safety and tolerability of the transition from EU RPP to M923 as compared with continuous use of EU RPP with regard to AEs will be evaluated with a summary of all TEAEs by treatment arm and by treatment period:

- Period 1 from Week 0 to Week 16 (included)
- Period 2 from Week 16 to Week 25 (included)
- Period 3 from Week 25 to Week 37 (included)
- Period 4 from Week 37 to Week 48 (included)
- Follow-up

Physical examination, vital signs, laboratory parameters, and ECGs will be presented by treatment group for each visit. Descriptive statistics of value and change from baseline will be provided for vital signs and laboratory parameters.

The clinical safety and tolerability of the transition from EU RPP to M923 as compared with continuous use of EU RPP with regard to all safety endpoints will be evaluated using the descriptive statistics provided over time.

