2. STUDY DESIGN

This study is a Phase 3, active-controlled, randomized, double-blind, multicenter study to determine the clinical equivalence between M923 (a proposed adalimumab biosimilar) and EU RPP.

The subject participation period is approximately 56 weeks (4-week screening period, 48-week treatment period, and 4-week follow-up period) from enrollment to subject completion (i.e., last study visit), unless prematurely withdrawn.

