5.5 Changes from the Planned Statistical Analysis in Protocol

There are no significant changes from the planned statistical analysis in the protocol.

The PP Analysis Set definition has been amended to clarify that only those protocol deviations that are deemed significant enough to affect the primary analysis will result in exclusion from this population.

The modified Intention-To-Treat (mITT) Analysis Set has been added as an additional supplementary analysis for Primary Analysis.

Health Outcome Variables

CCI

Clinical Safety and Tolerability

The protocol specified that the clinical safety and tolerability of the transition from EU RPP to M923 as compared with continuous use of EU RPP with regard to AEs will be evaluated with a summary of all TEAEs by treatment arm and by treatment period. However, the number of periods for analysis was redefined to display results

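### SAP 8.1 closes the TEAE window at Week 48 for completers, so the Follow-up row of its own TEAE-by-period table is all but shut to them; the effect is confined to TEAE-labelled tables

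*SAP*

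**What the plan says.** SAP 8.1 defines TEAEs as events that begin or worsen from the first dose onward, "until study completion/withdrawal (Week 48) or 30 days following the last M923 or EU RPP treatment for early withdrawn subjects". The post-dose extension belongs to early withdrawals alone. As its AE evaluation of the move from EU RPP to M923, the section then plans a table of TEAEs by arm and period. The last treatment row is "Period 4 from Week 37 to Week 48 (included", and a Follow-up row, which is not defined, comes after it.

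Two other sentences in SAP 8.1 speak of AEs rather than TEAEs. One plans an overview by treatment group: "The number and percentage of subjects with any AE, any related AE, any severe AE, any related severe AE, any SAE", and so on. The other sets a different limit: "Any adverse events reported more than 30 days after a subject has completed or withdrawn early from the study, will not be summarized". Events beyond that limit are only listed.

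Completion has two meanings. Protocol 10.3.3 attaches study completion to the Week 48 end-of-treatment visit. SAP 2 counts a screening period, a treatment period "and 4-week follow-up period) from enrollment to subject completion (i.e., last study visit".

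The protocol also gives two AE windows. Section 12.1.2 has treatment-emergent events recorded on the eCRF "until study completion/discontinuation (Week 48) or 4 weeks following the last M923 or EU RPP treatment (for early termination subjects". Section 13.4.4.2 sets no end: "Treatment-emergent adverse events (TEAEs) are defined as AEs that started or worsened in severity on or after the first dose of study medication". It prints the same five rows, including Follow-up. Protocol 10.3.4 schedules AE monitoring at the Week 52 visit and keeps only later information off the eCRF.

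SAP 5.5 says of the AE periods: "However, the number of periods for analysis was redefined to display results". The available text stops there.

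**The concern.** A table of TEAEs can hold only events that meet the TEAE definition. If the definition stops on the day the last treatment period stops, the next row has nothing to count for those subjects. Under Protocol 13.4.4.2 the row can be filled, because that definition is open-ended. The SAP brought in the Week 48 limit of Protocol 12.1.2 and kept the row.

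At stake is what the row would mean. It would look like post-treatment safety for each arm but would hold few or no events from subjects who finished treatment, and a near-empty row could be taken as reassurance about them. The TEAE tables and the overview of any AE and any SAE could also give different counts for the same subjects with no stated reason, and two programmers could reasonably choose different cut-offs.

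**Working it through.** **Study days.** Study day = 7 × week + 1. This gives 113, 176, 260, 337 and 365 for Weeks 16, 25, 37, 48 and 52, matching the schedule tables. The last dose, at Week 47, is Day 7 × 47 + 1 = 330.

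**Completers, read literally.**
- The TEAE window ends at Week 48 = Day 337. Period 4 also ends at Week 48, inclusive = Day 337.
- Days left for Follow-up: 337 − 337 = 0.
- TEAE capture after the last dose: 337 − 330 = 7 nominal days.
- Planned safety follow-up after the last dose: 365 − 330 = 35 days, of which Days 338 to 365 (28 days; 28/35 = 80%) lie outside the TEAE window.
- The Week 48 visit may fall on Days 334 to 340 (±3). If the TEAE window ends at the actual visit and the periods end on the nominal day, a late visit leaves at most 340 − 337 = 3 days. The reverse mix with an early visit gives the same limit, 337 − 334 = 3.

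**Early withdrawals, last dose + 30 days, rows read as calendar weeks.**
- Last dose at Week 43 (Day 302): 302 + 30 = 332, before Day 337. A dose given 3 days late reaches 335, still before it.
- Last dose at Week 45 (Day 316): 346, so 346 − 337 = 9 days in Follow-up.
- Last dose at Week 47 (Day 330): 360, so 360 − 337 = 23 days.
- Any last dose before Week 43 ends earlier still.

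If Follow-up instead means the time after each subject's own treatment ended, any early withdrawal can contribute.

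**The 30-day sentence on AEs.** If completion is Week 48, its cut-off is 337 + 30 = Day 367. If completion is the last study visit, it is 365 + 30 = Day 395. Both are later than nominal Week 52, so this sentence implies that completers' Week 48 to 52 AEs are summarized somewhere. It does not make them TEAEs.

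**The two documents on early terminations.** The SAP allows 30 days and Protocol 12.1.2 allows 4 weeks = 28 days, a difference of 2 days.

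**The case against.** The strongest reply is that little is lost. SAP 5.4 runs the second analysis period from after Week 16 to the end of the study. SAP 8 summarizes safety data by that period, and the 30-day sentence shuts out of summaries only AEs reported well after completion. Together these support counting completers' Week 48 to 52 events in the AE-labelled tables, and SAP 8.1 lists every AE in any case. This stands, and it confines the defect to tables labelled TEAE.

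SAP 5.5 also breaks off where it reports that the periods were redefined, so the missing words might retire the Follow-up row. That cannot be settled from the text available. SAP 8.1 still prints the row, so the conflict in wording remains, but which table would be produced is less certain.

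Completion might mean the last visit, as in SAP 2. This does not help, because the TEAE definition prints Week 48 next to the word and Protocol 10.3.3 uses it in the same way.

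A reader might infer that post-treatment events in completers vanish from the report, or that the comparison of switching with continued EU RPP is distorted. The documents do not support either. The B2 switches at Weeks 17, 25 and 37 fall in Periods 2 to 4, which are unaffected; Follow-up starts 48 − 37 = 11 weeks after the last switch. The same end rule applies to all arms, and nothing in the documents shows that it favours one of them.

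**Conclusion.** The inconsistency is real and narrow. As written, SAP 8.1 gives completers 7 nominal post-dose days of TEAE capture and early withdrawals 30. It also plans a Follow-up row to which completers can contribute 0 days, or at most 3 under mixed date conventions. On a calendar reading only withdrawals last dosed at Week 45 or 47 reach the row; on a reading relative to each subject's end of treatment, any early withdrawal does. The primary endpoint is not touched.

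This assumes that Week 48 in the definition means what it says and that the five printed periods are the ones to be used. The documents give no event counts, so the number of events affected is unknown. The point lies between a minor correction and one that should be made. Confidence is moderate because the text of SAP 5.5 is incomplete.

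**What to change.** Before unblinding, give SAP 8.1 one TEAE end rule for all subjects that covers the planned safety follow-up. One option is to run the window through the last study visit: the Week 52 visit for completers, and for discontinuing subjects the visit planned 5 weeks after last dose. A stated number of days after last dose would apply where that visit is missed. Then define Follow-up by the same rule, align the 30-day sentence on AEs, and record the change in SAP 5.5. SAP 5.1 makes this document serve both the interim and the final report, so the rule should be the same in both.

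Extending 30 days to completers would stop at 330 + 30 = Day 360, short of Week 52. A fixed 35 days reaches Day 365 but leaves out later events found at a late Week 52 visit, which the ±2-week window allows up to Day 379. Ending at the visit keeps them.

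The protocol needs attention too. Section 12.1.2 ties eCRF recording to Week 48, or 4 weeks after last dose for early terminations, while Section 10.3.4 plans AE monitoring at Week 52. These must be reconciled, and the sponsor should confirm that Week 48 to 52 AEs are on the eCRF. A reader might take this to be a SAP-only edit; because of that conflict, a protocol clarification may be needed. The visit after discontinuation also depends on the subject's agreement (Protocol 10.6), hence the fallback rule.

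The cost is one definition, two aligned statements and an entry in SAP 5.5, with no new visits. TEAE counts may rise slightly.

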8.7.3 Description of Treatment

Subjects will be administered 80 mg of M923 or EU RPP at Week 0 and then 40 mg every 2 weeks (Q2W) starting at Week 1 of the study. Self-injections should occur on the same day (\pm 3 days) each treatment week according to a predetermined randomization schedule with 2 arms indicated as follows:

- Arm A: M923 from Weeks 0 to 48 (n = 258 subjects)
- Arm B: EU RPP from Weeks 0 to 16 (last dose at Week 15); then randomized again at Week 16 into Arms B1 and B2:
 - Arm B1: Continues EU RPP from Weeks 17 through 48 (last dose at Week 47; n = up to 129 subjects)
 - Arm B2: Transition to M923 at Week 17; then to EU RPP at Week 25; and to M923 at Week 37 (last dose at Week 47; n = up to 129 subjects)

At Weeks 0, 1, 17, 19, 21, 25, 27, 37, and 39, injections will be administered in the clinic after all required assessments and blood sample collections have been completed.

All other injections will be administered by the subjects or caregiver at home (but after assessments completed if a planned injection date coincides with a planned visit date [Weeks 29, 33, 41, and 45]). When injection occurs in the clinic, subjects should be observed for 2 hours in the clinic post-injection at Weeks 0, 1, 17, 25, and 37; at Weeks 19, 21, 27, and 39, subjects should be observed for 30 minutes after injection.

At any time during the study, any of the IPs may be interrupted or discontinued at the discretion of the investigator based on his/her evaluation of the subject's condition or safety. No dose modification is permitted for this study.

When injection occurs in the clinic, the investigator or a qualified designee will evaluate the current injection sites 30 minutes (\pm 10 minutes) after study drug administration in the clinic at Weeks 0, 1, 17, 19, 21, 25, 27, 37, and 39.

They should also evaluate immediately prior injection site at each subsequent visit as applicable ([Section 12.10](#)). For injections given at home, injection site reactions will be recorded in the subject diary ([Section 10.5](#)). There will be no injection at Week 48 (Visit 19), but injection site evaluation for previous injections will occur.

Any injection site reactions, regardless of causality, will be recorded on the AE electronic case report form (eCRF). Any concomitant medications, including those used to treat AE(s), will be recorded on the appropriate eCRF.

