5.4 Analysis Periods

Analysis periods will be defined using the two randomization dates. The first analysis period (Week 0 to Week16) is defined from the Week 0 visit to the end of Week 16 visit. The second analysis period (>Week 16) is defined as starting after Week 16 to the end of the study.

For the first analysis period (Week 0 to Week 16), summary tables will be displayed by treatment arm A and B. For the second analysis period (>Week 16), summary tables will be displayed by treatment arm A, B1, and B2.

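### The transition periods include their end week, so arm B2's same-day reactions to the Week 25 and Week 37 switch doses are counted in the period before the switch; Period 2 also opens before any M923 is given

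*SAP*

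**What the plan says.** SAP 8.1 names a summary of treatment-emergent adverse events by arm and treatment period as the adverse-event evaluation of the transition from EU RPP to M923. Its second period is "Period 2 from Week 16 to Week 25 (included" and its third is "Period 3 from Week 25 to Week 37 (included", each with the bracket closed after that word. Period 4 runs from Week 37 to Week 48 on the same pattern. Protocol 13.4.4.2 lists identical periods. Neither section says whether the start week is excluded.

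SAP 5.4 sets a separate two-period split around re-randomization. Its first period "is defined from the Week 0 visit to the end of Week 16 visit" and its second "is defined as starting after Week 16 to the end of the study".

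The dosing is in Protocol 8.7.3: "Arm B2: Transition to M923 at Week 17; then to EU RPP at Week 25; and to M923 at Week 37". The same section states: "At Weeks 0, 1, 17, 19, 21, 25, 27, 37, and 39, injections will be administered in the clinic after all required assessments" and blood sampling. After an in-clinic dose, "the investigator or a qualified designee will evaluate the current injection sites 30 minutes" later, and subjects are observed for two hours at Weeks 17, 25 and 37.

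For immunogenicity, Protocol 13.4.4.3 counts subjects with at least one positive ADA result by arm and by these periods; SAP 10 uses periods similar to them. Footnote j of the SAP 15.2 schedule puts sampling before dosing. SAP 9 assigns the Week 21 and 25 troughs to B2's first M923 phase, Weeks 29 and 37 to the return to EU RPP, and Week 41 to the second M923 phase.

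**The concern.** Evaluating the transition is a secondary objective, and reactions soon after the first dose of a different product are part of what it is meant to reveal. Weeks 25 and 37 are the right weeks to cut at. The difficulty is the side on which the dose day falls. With the end week included, an immediate reaction to B2's second switch to M923, at Week 37, is tabulated with a period in which B2 is otherwise on EU RPP. An immediate reaction to the Week 25 EU RPP dose is tabulated with the M923 period.

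Two smaller matters go with it. Period 2 starts at Week 16 although M923 starts at Week 17. And the by-period ADA count includes subjects who were already positive before the switch, whereas the outcome in Protocol 8.4.2.3 and SAP 3.3 is seroconversion following the transition.

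**Working it through.** The plan gives no figure to reproduce, so the check assigns scheduled events to periods.

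**Inputs.** Scheduled study days are in SAP 15.2: Week 16 = Day 113, Week 17 = 120, Week 25 = 176, Week 37 = 260, Week 48 = 337 (day = 7 × week + 1). Injections after re-randomization fall on odd weeks from 17 to 47 (SAP 15.2, footnote n). The ADA samples relevant here are at Weeks 17, 21, 25, 29, 37, 41 and 48.

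**B2 injections by boundary rule.**

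| Rule | Period 2 | Period 3 | Period 4 |
|---|---|---|---|
| End week in, start week out | 17, 19, 21, 23 M923; **25 EU RPP** | 27, 29, 31, 33, 35 EU RPP; **37 M923** | 39 to 47 M923 |
| Both weeks in | 17 to 23 M923; **25 EU RPP** | 25 to 35 EU RPP; **37 M923** | 37 to 47 M923 |
| Start week in, end week out | 17 to 23 M923 | 25 to 35 EU RPP | 37 to 47 M923 |

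Under the first rule, 1 of 5 injections in Period 2 and 1 of 6 in Period 3 are the incoming product. Under the second, the same two doses still sit in the earlier period (1 of 5 and 1 of 7) and are counted again in the next. Only the third rule gives B2 one product per period, and it contradicts the stated inclusion of the end week. The Week 17 dose falls in Period 2 under every rule and is correctly placed.

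**In-clinic injections, first rule.** Period 2 has Weeks 17, 19, 21 and 25, so 1 of 4 is EU RPP. Period 3 has Weeks 27 and 37, so 1 of 2 is M923. These are the injections with the 30-minute post-dose evaluation. Staff also review the immediately prior injection site at later visits (Protocol 8.7.3). That adds the home injections of Week 23 (reviewed at Week 25), Week 31 (at Week 33) and Week 35 (at Week 37), and the shares become 1 of 5 and 1 of 4.

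**Days, first rule.** Period 2 is Days 114 to 176, or 63 days. Days 114 to 119 precede M923: 6/63 = 9.5%. If Day 113 also counts, it is 7/64 = 10.9%. With the ±3-day windows, the gap from the Week 16 visit to the Week 17 dose can be 1 day (117 − 116) to 13 days (123 − 110). Period 3 is Days 177 to 260, or 84 days, and the Week 37 dose day is 1/84 = 1.2% of it.

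**ADA samples, first rule.** Period 2 holds Weeks 17, 21 and 25. The Week 17 sample is pre-dose, so 1 of 3 precedes any M923. The Week 25 and Week 37 samples are also pre-dose and belong to the phase that is ending, which is where the periods and SAP 9 both put them.

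**The case against.** Several objections have force.

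- **The boundary is not fully specified.** SAP 5.4 concerns a different split and does not settle Weeks 25 or 37. This stands, but whether or not the start week is included, the switch-day reaction is counted in the earlier period. What remains open is only whether it is also counted in the later one.
- **Tables are by arm and period, not by product.** A reader might infer that reactions are attributed to the wrong product or moved between arms. The documents do not support that: the events stay in the B2 column and are compared with B1 under the same boundaries. What is lost is the correspondence between period and product in B2.
- **The in-clinic share is tempting.** A reader might infer that half of the staff-evaluated injections in Period 3 are M923. That ignores staff review of prior home-injection sites. Home reactions also go into the diary, and every injection site reaction is recorded as an adverse event.
- **Some switch-day findings belong to the outgoing product.** Protocol 10.3.2 places adverse event monitoring, examination, vital signs, ECG and laboratory sampling before the injection. This stands, so moving the whole day to the new period would create the opposite error.
- **The early days of Period 2 might be read as bias.** B1 and B2 are both on EU RPP then, so the comparison is diluted and not biased.
- **Other outputs help.** Adverse-event tables for all time after Week 16, ADA by scheduled assessment, time to seroconversion and listings with onset dates are planned. SAP 10 foresees an analysis of predose-negative subjects, though only as an option and not tied to Week 17.
- **SAP 5.5 mentions redefined periods.** Its sentence breaks off in the available text, so a further rule cannot be excluded. SAP 8.1 nevertheless still lists the protocol's periods.

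**Conclusion.** The point holds as a minor defect in the period definitions. In the table that SAP 8.1 names for evaluating the transition, same-day reactions to two of B2's three switch doses are counted in the period before the switch, and possibly twice. One of those two doses is the second switch to M923. Period 2 also carries 6 to 7 scheduled pre-switch days and one pre-switch ADA sample, which dilutes its B2 versus B1 comparison.

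The ADA point is smaller still. A by-period count of any positive result mixes existing positives with new ones. The documents give no ADA rate, so the size of that effect is unknown.

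All of these outputs are descriptive and the Week 16 primary analysis is unaffected. The conclusion rests on scheduled visit days, on full dosing in B2, and on SAP 5.5 containing no further boundary rule.

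**What to change.** These changes concern the analysis only.

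1. Make the adverse-event periods non-overlapping, starting at the actual Week 17, 25 and 37 dose dates. Use the scheduled visit date where the dose was not given, since Protocol 8.7.3 says "any of the IPs may be interrupted or discontinued at the discretion of the investigator"; every re-randomized subject is then kept. Show the interval from after the Week 16 visit to the Week 17 dose separately.
2. Place injection site reactions and other adverse events with onset on a switch day in the new period, except events recorded as starting before the injection or found at the pre-injection assessments. State that this is a convention, because the SAP 8.1 listing gives onset date and not time.
3. Keep pre-dose ADA samples with the interval that is ending, as SAP 9 does for troughs, and treat Week 17 as pre-switch.
4. Beside the planned table, report new ADA and new neutralizing ADA positives after Week 17 among B1 and B2 subjects negative at all samples through the Week 17 pre-dose sample.
5. As a minor text correction, amend the SAP 8.1 tabulation that names only Arms A and B2 after Week 16 so that it includes B1, as SAP 5.4 and SAP 8 require.

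The cost is SAP wording and programming. SAP 6.5 already uses dose dates, and onset dates are already listed. The pre-switch interval adds a column. The table in item 4 has a smaller denominator: with up to 129 planned subjects per arm and an assumed share q already positive by Week 17, it is 129 × (1 − q), about 116 at q = 0.1, 90 at 0.3 and 39 at 0.7. These q values are illustrations, not figures from the documents.
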